## 7.6 Special circumstances

Given that the average time to respond to decitabine with venetoclax is 1.3 months, it is possible that many patients could achieve a CR or CRI within this time yet also experience a DLT. Patients who achieve a CR or CRI within the this average 1.3 months' time to response, yet also experience a DLT, will be evaluated and treated at the discretion of the PI and sponsor. These patients will not automatically be taken off study, as we do not want to discontinue a study treatment that is providing benefit without determining if the specific DLT is significant enough to

warrant this.

If a patient experiences a DLT attributed to nivolumab requiring the use of high dose steroids ( $\geq 20$  mg prednisone daily, or the equivalent), they will be allowed to continue on study receiving decitabine with venetoclax.

## 8. PHARMACEUTICAL INFORMATION

A list of the adverse events and potential risks associated with the commercial agents administered in this study can be found in Section 10.1.

### 8.1 Investigational Agent

#### 8.1.1 Nivolumab

**Description:** Nivolumab Injection is a clear to opalescent, colorless to pale yellow liquid; light (few) particulates may be present. The drug product is a sterile, nonpyrogenic, single-use, isotonic aqueous solution formulated in sodium citrate dihydrate, sodium chloride, mannitol, diethylenetriaminepentacetic acid (pentetic acid), polysorbate 80 (Tween® 80), and water for injection. Dilute solutions of hydrochloric acid and/or sodium hydroxide may be used for pH adjustment (pH 5.5-6.5).

**Preparation:** Nivolumab injection can be infused undiluted (10 mg/mL) or diluted with 0.9% Sodium Chloride Injection, USP or 5% Dextrose. When the dose is based on patient weight (i.e., mg/kg), nivolumab injection can be infused undiluted or diluted to protein concentrations as low as 0.35 mg/mL. When the dose is fixed (eg, 240 mg, 360 mg, or 480 mg flat dose), nivolumab injection can be infused undiluted or diluted so as not to exceed a total infusion volume of 160 mL. For patients weighing less than 40 kilograms (kg), the total volume of infusion must not exceed 4 mL per kg of patient weight. During drug product preparation and handling, vigorous mixing or shaking is to be avoided. Nivolumab infusions are compatible with polyvinyl chloride (PVC) or polyolefin containers and infusion sets, and glass bottles.

**Storage:** Vials of Nivolumab injection must be stored at 2°- 8°C (36°- 46°F) and protected from light and freezing. The unopened vials can be stored at room temperature (up to 25°C, 77°F) and room light for up to 48 hours.

If a storage temperature excursion is identified, promptly return Nivolumab to 2°C-8°C and quarantine the supplies. Provide a detailed report of the excursion (including documentation of temperature monitoring and duration of the excursion) to [contact] for determination of suitability.

**Stability:** Refer to the package label for expiration.

The administration of undiluted and diluted solutions of Nivolumab must be completed within 24 hours of preparation. If not used immediately, the infusion solution may be stored up to 24 hours in a refrigerator at 2°-8°C (36°-46°F) and a maximum of 8 hours of the total 24 hours can be at

room temperature (up to 25°C, 77°F) and room light. The maximum 8-hour period under room temperature and room light conditions includes the product administration period.

**CAUTION:** The single-use dosage form contains no antibacterial preservative or bacteriostatic agent. Therefore, it is advised that the product be discarded 8 hours after initial entry.

**Route of Administration:** Intravenous infusion over 30 minutes. Do not administer as an IV push or bolus injection.

**Method of Administration:** Administer through a 0.2 micron to 1.2 micron pore size, low-protein binding (polyethersulfone membrane) in-line filter.

**Agent Ordering:** Nivolumab is supplied by Bristol-Myers Squibb for this study and distributed by the Pharmaceutical Management Branch, CTEP/DCTD/NCI as 100 mg vials (10 mg/mL) with a 0.7mL overfill. It is supplied in 10 mL type I flint glass vials, with fluoropolymer film-laminated rubber stoppers and aluminum seals

## 8.2 Agent Ordering and Agent Accountability

### Availability

NCI-supplied agents may be requested by eligible participating Investigators (or their authorized designee) at each participating institution. The CTEP-assigned protocol number must be used for ordering all CTEP-supplied investigational agents. The eligible participating investigators at each participating institution must be registered with CTEP, DCTD through an annual submission of FDA Form 1572 (Statement of Investigator), NCI Biosketch, Agent Shipment Form, and Financial Disclosure Form (FDF). If there are several participating investigators at one institution, CTEP-supplied investigational agents for the study should be ordered under the name of one lead participating investigator at that institution.

Submit agent requests through the PMB Online Agent Order Processing (OAOP) application. Access to OAOP requires the establishment of a CTEP Identity and Access Management (IAM) account and the maintenance of an “active” account status, a “current” password, and active person registration status. For questions about drug orders, transfers, returns, or accountability, call or email PMB any time. Refer to the PMB’s website for specific policies and guidelines related to agent management.

**Drug Returns:** All unused drug supplies must be returned to the PMB. When it is necessary to return study drug (e.g., sealed vials remaining when a patient permanently discontinues protocol treatment, expired vials recalled by the PMB), investigators must return the study drug to the PMB using the NCI Return Agent Form available on the NCI home page (<http://ctep.cancer.gov>) or by calling the PMB at [contact].

**Drug Accountability:** The investigator, or a responsible party designated by the investigator, must maintain a careful record of the receipt, disposition, and return of all drugs received from the PMB using the NCI Investigational Agent Accountability Record available on the NCI home page (<http://ctep.cancer.gov>) or by calling the PMB at [contact]. A separate NCI Investigational Agent Accountability Record must be maintained for each patient sequence number and for each agent on this protocol.

**Investigator Brochure Availability:** The current versions of the IBs for the agents will be accessible to site investigators and research staff through the PMB OAOP application. Access to OAOP requires the establishment of a CTEP IAM account and the maintenance of an “active” account status, a “current” password and active person registration status. Questions about IB access may be directed to the PMB IB Coordinator via email.

## 8.3 Commercial Agent

### 8.3.1 Decitabine

**Description:** Decitabine (Dacogen) is supplied as a sterile, lyophilized white to almost white powder, in a single-dose vial, packaged in cartons of 1 vial. Each vial contains 50 mg of decitabine.

**Preparation:** Reconstitution with 10 mL of Sterile Water for Injection results in a concentration of 5 mg/mL. Immediately after reconstitution, the solution should be further diluted with infusion fluids, such as 0.9% sodium chloride Injection or 5% dextrose injection to a final drug concentration of 0.1 - 1 mg/mL.

Unless used within 15 minutes of reconstitution, the diluted solution must be prepared using **COLD** infusion fluids (2°C - 8°C) and stored at 2°C - 8°C for a maximum of 4 hours. Diluted stored solution must be used within 4 hours from the time of preparation.

Use the diluted, refrigerated solution within 4 hours from the time of preparation or discard.

**Storage:** Store vials at 25°C (77°F), excursions permitted to 15-30°C (59-86°F).

**Stability:** Refer to the package label for vial expiration. Refer to Preparation (above) for infusion stability.

**Route of Administration:** Intravenous

**Agent Ordering:** The agent is commercially available.

### 8.3.2 Venetoclax

**Description:** Venetoclax tablets are supplied as oblong, bi-convex pale yellow or beige tablets that contain 100 mg venetoclax as the active ingredient. Each tablet also contains the following inactive ingredients: copovidone, colloidal silicon dioxide, polysorbate 80, sodium stearyl fumarate, and calcium phosphate dibasic, iron oxide yellow, polyvinyl alcohol, polyethylene glycol, talc, and titanium dioxide. Each tablet is debossed with “V” on one side and a “100” corresponding to the tablet strength on the other side. The 100 mg tablets are available in 120 and 180 count bottles.

**How Supplied:** 10 mg, 50 mg, 100 mg tablets

**Storage:** Store at or below 86°F (30°C).

**Stability:** Refer to the package label for expiration.

**Route(s) of Administration:** oral with a meal and water at approximately the same time each day. Venetoclax tablets should be swallowed whole and not chewed, crushed, or broken prior to swallowing.

**Agent Ordering:** agent is commercially available

## 9. STATISTICAL CONSIDERATIONS

### 9.1 Study Design/Endpoints

This will be a phase 1 study determining the maximum tolerated dose (MTD) with an expansion cohort examining the signal for efficacy will be conducted for this study.

Adult AML patients ( $\geq 18$  years) with relapsed or refractory disease are eligible. All patients on study must have primary refractory disease following at least one induction regimen or have relapsed disease following induction or consolidation or aHSCT.

Nivolumab in a fixed dose will be administered in combination with decitabine and venetoclax. For the induction phase of this study, patients will be treated with 10 days of decitabine the first 10 days of the cycle. Patients can be treated with up to 3 cycles of 10-day decitabine course before moving on to the maintenance phase of the study. For the maintenance phase, patients will be treated with 5 days of decitabine the first 5 days of the cycle and this treatment will continue until one of the following occurs: loss of response/disease progression, bone marrow/stem cell transplantation, unacceptable toxicities, or patient withdrawal.

For all patients on study, if CR, CRi, or CRh is achieved during cycles 1-3, patients will continue on study at the time response is noted with the maintenance phase treatment. If no response is achieved by cycle 3,

patients will come off study. Bone marrow biopsy will occur on Day 28 (+/- 2 days) for up to 3 cycles to determine treatment response, then Day 28 (+/- 2 days) every third cycle.

Three dose levels (DL 1, -1, -2) illustrated in [Section 6.1](#) are to be examined, and 3+3 design will be used to determine the safe and tolerable dose level. DLT will be defined in [Section 6.4](#), and DLT observation period will be defined as the time period from the start of nivolumab therapy on C1D15 to the end of cycle 3 (can include induction and maintenance cycles based on how many induction cycles are needed). Dose escalation process will follow the rules specified below. Patients who do not finish DLT observation period due to reasons other than DLT will need to be replaced.

Number of Subjects with DLT at a Given Dose Level	Escalation Decision Rule
0 out of 3	Enter 3 subjects at the next dose level.
1 out of 3	
Enter 3 more subjects at this dose level.
 
 
• If 0 of these 3 subjects experience DLT, proceed to the next dose level.
 
• If 1 or more of this group suffer DLT, then dose escalation is stopped, and this dose is declared the maximally administered dose. Three (3) additional subjects will be entered at the next lowest dose level if only 3 subjects were treated previously at that dose.
 

$\geq 2$	Dose escalation will be stopped. This dose level will be declared the maximally administered dose (highest dose administered). Three (3) additional subjects will be entered at the next lowest dose level if only 3 subjects were treated previously at that dose.
$\leq 1$ out of 6 at highest dose level below the maximally administered dose	This is generally the recommended maximally tolerated dose. At least 6 subjects should be entered at the recommended phase 2 dose.

We expect to enroll a minimum of 6 patients (6 patients treated at DL 1 with 1 or less patient experience DLT) and a maximum of 18 patients (6 at each of the DL 1, -1 and -2) for dose finding part. Once the MTD is determined, patients will be accrued to the expansion cohort to be treated at MTD. Including 6 patients treated at MTD from the dose escalation part, we plan to accrual additional 24 R/R AML patients to the expansion cohort. A total of 30 patients will be treated at MTD to decide whether the response rate (CR rate), P, is less than or equal to 30% (combination drug not of interest) or greater than or equal to 50% (combination drug is promising). If the number of responses out of 30 patients is 13 or more, the hypothesis that  $P \leq 30\%$  is rejected with a target error rate of 0.10 and an actual error rate of 0.084. If the number of

responses is 12 or less, the hypothesis that  $P \geq 50\%$  is rejected with a target error rate of 0.20 and an actual error rate of 0.181.

To estimate the response rate, defined by CR/Cri, which will be assessed by bone marrow biopsy after cycle 1, cycle 2, cycle 3, then every 3 cycles after this, and at time of relapse. Since this will study will only have a small sample size, it will not be powered to determine an accurate response rate for nivolumab in combination with venetoclax and decitabine. We will plan to estimate response rate, as defined by CR/CRI in all evaluable patients in this study, regardless of dose level of venetoclax, and will not attempt to evaluate response rate for individual dose levels. The response rate along with an exact 95% confidence interval will be reported. However, we can consider our study's response rate in context of recent retrospective studies evaluating venetoclax in combination with HMA as well as the historical response rate with high dose cytarabine-containing regimens where the CR rate is 30-40%. Therefore, a response rate of 50% would be considered promising.

Toxicity will be graded and reported according to the revised NCI Common Terminology Criteria for Adverse Events (CTCAE) version 5.0. All patients who receive any amount of the study drug (Nivolumab) will be evaluable for toxicity.

Dosing schema and dosing alterations can be found in [Section 6.1](#) and [Section 7](#).

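### Section 9.1 contradicts itself: its decision table is an upward 3+3, but its 6-patient minimum requires DL 1, the highest level, to be treated first

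*Combined protocol and SAP*

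**What the plan says.** Section 9.1 names a 3+3 design over three levels, DL 1, -1 and -2, and hands the conduct to a table: "Dose escalation process will follow the rules specified below". The rows of that table are:

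- No DLT in three: "Enter 3 subjects at the next dose level".
- One DLT in three: treat three more at the same level. Then, "If 0 of these 3 subjects experience DLT, proceed to the next dose level". With one or more further DLTs, escalation stops.
- Two or more DLTs: escalation stops and this level becomes the maximally administered dose. In both stopping cases, "Three (3) additional subjects will be entered at the next lowest dose level if only 3 subjects were treated previously at that dose".
- MTD row: at most one DLT "out of 6 at highest dose level below the maximally administered dose" is generally the recommended dose. A further sentence in that row asks for no fewer than six patients at the phase 2 dose.

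The narrative below the table gives the expected size. Its lower end reads: "We expect to enroll a minimum of 6 patients (6 patients treated at DL 1 with 1 or less patient experience DLT". Its upper end is put as "a maximum of 18 patients (6 at each of the DL 1, -1 and -2) for dose finding part". On what comes after dose finding, the narrative says: "Once the MTD is determined, patients will be accrued to the expansion cohort to be treated at MTD".

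The dose level table in Section 6.1 holds decitabine and nivolumab constant and varies the days of venetoclax. In cycle 1, dosing runs to day 28 at DL 1, day 21 at DL -1 and day 14 at DL -2. DL 1 is therefore the highest level, and none lies above it.

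**The concern.** The table and the narrative stand in the same section and describe different procedures. The table climbs to higher levels after tolerated cohorts, and goes back down only to a level that has already been treated. The narrative's smallest trial treats DL 1 and nothing else, and its largest uses all three levels.

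The MTD is the primary objective (Section 1.1), and it fixes the dose for the 24 additional patients of the expansion cohort. If the table cannot be run from the level that the narrative implies, cohort decisions on safety would have to be improvised or recorded as deviations.

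**Working it through.** **Inputs.** Three levels with DL 1 highest (Section 6.1). Cohorts of three, six at the recommended dose, stated minimum 6, stated maximum 18, expansion of 24 (all Section 9.1). Stated total 42 (Section 9.2). Counts exclude patients replaced for not completing the DLT period. No DLT rate is needed.

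**Step 1: reproduce the plan's counts.** Suppose DL 1 is treated first, a level with at most 1 DLT in 3 is filled to six, and two or more DLTs move the trial one level down. Section 9.1 does not print this rule; it is used here only to see what yields the stated figures.

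- Minimum: 3 + 3 = 6, all at DL 1 with 0 or 1 DLT.
- Maximum: 3 levels × 6 = 18.
- With expansion: 6 + 24 = 30 and 18 + 24 = 42.

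Enumerating every path under this rule gives a range of 6 to 18, and the 6 arises only when DL 1 is the MTD.

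**Step 2: try the upward direction that the table describes.** The fewest patients that put six at DL 1 are:

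| First level treated | Fewest patients in total |
|---|---|
| DL 1 | 6 |
| DL -1 | 3 + 6 = 9 |
| DL -2 | 3 + 3 + 6 = 12 |

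Only the first row meets the stated 6. An upward trial can also end with six or fewer patients, for example after 2 DLTs in 3 at DL -2. It then has no MTD and nobody at DL 1, so that is not the narrative's minimum. The maximum does not discriminate: upward from DL -2 also reaches 6 + 6 + 6 = 18. The contradiction rests on the 6 alone.

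**Step 3: run the printed table from DL 1.**

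| Result at DL 1 | Table's instruction | Can it be carried out? | Treated so far |
|---|---|---|---|
| 0/3 | go to the next level | no level above DL 1 | 3 |
| 1/3 | three more at DL 1 | yes | 6 |
| 1/3, then 0/3 | go to the next level | no level above DL 1 | 6 |
| 1/3, then 1 or more of 3 | stop; add three one level down if exactly three were treated there | stop, yes; DL -1 has 0 patients, so it is not opened | 6 |
| 2 or more of 3 | as above | as above | 3 |

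The most the table can treat is 3 + 3 = 6, all at DL 1. The stated maximum is 18, so the table has no route to the other 18 - 6 = 12 patients, at DL -1 and DL -2.

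**Step 4: the MTD row.** It describes a level below the maximally administered dose, so it does not describe DL 1 as the MTD. Yet DL 1 as the MTD is the outcome that gives the narrative's minimum.

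**Step 5: the response rule.** With 13 or more responses in 30, the error rates recompute as 0.0845 at a 30% response rate and 0.1808 at 50%. These agree with the stated 0.084 and 0.181, and the contradiction does not touch them.

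**The case against.** The strongest reply is that the intent is plain. The levels are numbered 1, -1, -2, and the narrative's minimum sits at DL 1. The Schema, the Regimen Description in Section 6.1 and the Section 11 calendar all give venetoclax on days 1-28 of induction, which is the DL 1 schedule. The narrative also stands below the sentence that introduces the rules, so it might count among them. Most of this stands. A reader might infer that the treatment text leaves the starting level open, because the background in Section 2.3.2 gives 400 mg only to day 21, which matches DL -1. That goes too far: one background paragraph departs from several operative passages. What remains is that no sentence names the starting level, and that the narrative gives patient counts, not actions after each cohort.

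A second reply is that the six-patient sentence in the MTD row justifies filling DL 1 to six after 0/3. It could. For the same reason a reader should not infer that the table forbids naming DL 1 as the MTD: the row is worded as what is generally the case, not as an exclusion. But the sentence gives no route to DL -1 or DL -2.

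A third is that the next level could mean the next in the list, DL -1. That would lower the dose after a tolerated cohort, and it conflicts with a minimum of six patients all at DL 1.

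A fourth is that no reading doses anyone above DL 1, since no such level exists. That is right, and the point does not claim otherwise.

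**Conclusion.** The contradiction holds. The stated minimum of 6 requires DL 1 first. From DL 1, the table has no level to move to after 0/3, or after 1/3 then 0/3, and no trigger to open DL -1 after two or more DLTs. Read literally, it treats at most 6 patients against a stated maximum of 18. This is a stated rule that cannot produce the stated counts, rather than a missing detail. The result rests on the level order in Section 6.1 and on counting without replacements; it assumes no DLT rate.

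Two stronger readings are not supported. A reader might infer that the silence on what follows if DL -2 is not tolerated is a further contradiction. It is an unstated outcome: expansion opens only after an MTD is determined, so without one it does not open. A reader might also infer that the sample size fails. The 30-patient rule and the total of 42 stand.

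**What to change.** The sponsor should reconcile the Section 9.1 table with the narrative beneath it by:

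- naming the starting level and the direction;
- stating one action for each DLT outcome at DL 1, -1 and -2, consistent with the counts of 6 and 18;
- wording the MTD row so that it covers every level that can be selected;
- adding, as a clarification, what follows if the lowest level is not tolerated.

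Separately, the venetoclax schedule in Section 2.3.2 must be reconciled with the Schema, both tables in Section 6.1 and the Section 11 calendar. Which rule and which schedule govern is for the sponsor to decide.

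The cost is amendment wording for one table and a few sentences, plus review time. A cohort decision that falls due meanwhile may have to wait. No extra patients are needed if the 6 and 18 are kept.

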## 1. OBJECTIVES

### 1.1 Primary Objectives

- 1.1.1 To obtain the safety and maximum tolerated dose (MTD) of decitabine and venetoclax in combination with nivolumab for relapsed/refractory (R/R) AML patients.

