### 6.3 Definition of Dose-Limiting Toxicity

The dose limiting toxicity period (DLT) will be defined as the time period from the start of nivolumab therapy on C1D15 to the end of cycle 3. DLT will be defined as non-hematologic toxicity of  $\geq$  grade 3 with the exception of grade 3 nausea and vomiting that resolves to  $<$  grade 3 within 72 hours, and infection (infection-related toxicities such as fever/sepsis, see below). The grade 3/4 toxicity, designated to be DLT, should be considered drug-related. Patients with transient grade  $\geq$  3 electrolyte abnormalities that are not clinically significant and are correctable within 24 hours will not be considered a DLT. Patients with  $\geq$  grade 3 transient liver function test abnormalities (AST, ALT, or alkaline phosphatase) that resolve to  $<$  grade 2 within 5 days will not be considered DLT only if it is self-limited without steroid treatment. Grade 3 or 4 infection will not constitute DLT unless it is felt that the infection resulted from unexpectedly complicated myelosuppression (degree or duration).

Hematological DLT will be considered as failure to recover neutrophil count (ANC $\geq$ 500), or platelet count  $\geq$ 25,000, or hemoglobin  $\geq$ 7 by Day 42 in patients with  $<$ 5% blasts in the bone marrow, absence of myelodysplastic changes, and/or absence of evidence of disease by flow cytometry in the bone marrow. For patients with  $\geq$  5% blasts, myelodysplastic changes, or evidence of disease by flow cytometry/cytogenetics, failure to recover neutrophil, platelet count, or hemoglobin may not be considered DLT as this could be the result of persistent disease.

Specifically with nivolumab, any patient who requires high dose steroids (any dose greater than the equivalent to 20 mg prednisone daily) will be considered to have experienced a DLT and will be taken off nivolumab but allowed to remain on decitabine and venetoclax.

Management and dose modifications associated with the above adverse events are outlined in Section 7.

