#### 6.3.1 Evaluable for toxicity

Patients evaluable for safety/toxicity: Any patient receiving study treatment during the DLT eval period- start of nivolumab C1D15 to end of cycle 3. Therefore, any patients who do not receive nivolumab will not be evaluable for safety and will be replaced.

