## 11. STUDY CALENDAR

Baseline evaluations are to be conducted within 10 days prior to start of protocol therapy. In the event that the patient's condition is deteriorating, laboratory evaluations should be repeated within 48 hours prior to initiation of the next cycle of therapy.

	Pre-Study	Induction cycle 1	Induction cycles 2-3 (If needed)	Maintenance cycles	Relapse/Off Study
Decitabine		D	D	D	
Nivolumab		N	N	N	
Venetoclax		V	V	V	
Informed consent	X				
Demographics	X				
Medical history	X				
Concurrent meds a	X	X	X	X	
Physical exam b	X	X	X	X	X
Vital signs c	X	X			X
Height	X				
Weight	X	X			X
Performance status d	X	X			X
Serum Chemistry e	X	X	X	X	X
CBC w/diff f	X	X	X	X	X
EKG	X				
Adverse event evaluation g	X	X	X	X	X
Pregnancy test h	X	X	X	X	
Bone marrow i	X	X	X	X	X
Correlative studies j	X	X	X	X	X

D: Decitabine will be given on Days 1-10 of Induction cycles and Days 1-5 of maintenance cycles

N: Nivolumab will be given on Day 15 of cycle 1 and Days 1 and 15 of all subsequent cycles

V: Venetoclax will be given on Days 1-28 of induction cycles and Days 1-21 of maintenance cycles. Dosing ramp-up on days 1-3 or 1-4 (based on concurrent use of CYP3A inhibitors as outlined in Section 6.3.1)

a: Concurrent medications should be assessed at screening and the beginning of each treatment cycle

b: Physical exam should be performed at Screening, Days 1 and 15 of every cycle and End of Treatment/Relapse

c: Vital signs should be performed at Screening, Days 1 and 15 of every cycle and End of Treatment/Relapse. Vitals signs include blood pressure, heart rate, temperature, oxygen saturation, and respiratory rate.

d: Performance status should be evaluated at Screening, Day 1 of each cycle of therapy, and End of Treatment/Relapse

e: Serum chemistry will include: Na, K, CO2, Cl, BUN, Cr, AST, ALT, AP, TB, TP, albumin, LDH, and uric acid should be performed at screening, pre-dose (within 4 hours prior to venetoclax administration), every 12 hours during venetoclax ramp-up period (see Appendix C for tumor lysis management guidelines), twice weekly otherwise during induction cycles and at the beginning of each maintenance cycle and relapse/EOT

f: CBC with differential. To be performed at screening, twice weekly during induction cycles, and at the beginning of each maintenance cycle and relapse/EOT.

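### Treated patients who die or permanently stop before their first nivolumab dose are in no toxicity analysis set

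*Combined protocol and SAP*

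**What the plan says.** The primary objective in Section 1.1 is "To obtain the safety and maximum tolerated dose (MTD) of decitabine and venetoclax in combination with nivolumab". Two places then define who counts for toxicity.

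- Section 9.1: "All patients who receive any amount of the study drug (Nivolumab) will be evaluable for toxicity".
- Section 6.3.1: "any patients who do not receive nivolumab will not be evaluable for safety and will be replaced".

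The study calendar in Section 11 fixes the timing.

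- "Nivolumab will be given on Day 15 of cycle 1 and Days 1 and 15 of all subsequent cycles".
- "Decitabine will be given on Days 1-10 of Induction cycles and Days 1-5 of maintenance cycles".
- "Venetoclax will be given on Days 1-28 of induction cycles and Days 1-21 of maintenance cycles".

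The DLT window in Section 6.3 runs "from the start of nivolumab therapy on C1D15 to the end of cycle 3". For the 3+3, Section 9.1 adds: "Patients who do not finish DLT observation period due to reasons other than DLT will need to be replaced".

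Three other provisions matter. Section 9.3 requires reports on the secondary objectives to include all patients on the study. Section 10.3.2 has all adverse events after baseline collected in the database. Section 10.3.4 requires any death on study to be reported whatever its cause.

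**The concern.** Treatment begins two weeks before a patient can enter the toxicity-evaluable set. Whether a patient enters it depends on what happens in those two weeks, so membership is partly decided by outcome. The protocol itself treats the start of therapy as hazardous: Section 6.4.2 regards every patient as high risk for tumour lysis and requires chemistry every 12 hours during the venetoclax ramp-up.

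At stake is the toxicity summary that answers the primary objective. That objective names the three-drug combination, and the regimen as scheduled starts on Day 1. A summary confined to nivolumab recipients describes toxicity given that the patient reached nivolumab. It does not describe toxicity among those who started the regimen.

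**Working it through.** **1. Exposure before a patient can be counted.** From Section 11, decitabine is scheduled on Days 1-10 and venetoclax daily from Day 1, with the first nivolumab on Day 15. That is 10 scheduled days of decitabine and 15 - 1 = 14 of venetoclax. Section 2.2.1 gives Day 14 for the first nivolumab dose. That passage and the calendar should be reconciled, but the point does not turn on one day.

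**2. Which set holds a patient who never receives nivolumab?**

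| Provision | Includes this patient? |
|---|---|
| 9.1, evaluable for toxicity | No |
| 6.3.1, evaluable for safety | No, and replaced |
| 9.1, 3+3 decision | No, replaced |
| 9.3, all-patient reports | Yes, but for the objectives of Section 1.2 only; safety is in Section 1.1 |
| 10.3.2, 10.3.4, 10.4, AE and death reporting | Yes, but this is data capture, not an analysis set |

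The parenthesis in the 9.1 sentence and the explicit exclusion in 6.3.1 rule out reading the study drug as any of the three agents.

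**3. Form of the bias.** Let d be the share of treated patients who never receive nivolumab, R_N the rate of some toxicity among those who do, and R_0 the rate among those who do not. The rate among all treated is

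R_all = (1 - d) x R_N + d x R_0, so R_all - R_N = d x (R_0 - R_N).

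The table reports R_N. For death before Day 15, R_N is 0 by construction, because such a patient cannot have had nivolumab. The table therefore shows none, whatever the true rate. For other toxicities the understatement is at most d x (1 - R_N), which cannot exceed d. Its size depends on why patients left.

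**4. The plan's own total.** Section 9.1 gives at most 18 patients in dose finding plus 24 more in expansion: 18 + 24 = 42, which agrees with Section 9.2. The sum has no allowance for replacements.

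**5. Chance and number of dropped patients.** The documents give no value for d. The nearest figure is the 3.6% 30-day mortality in Section 2.4.1, from the phase 2 study of 10-day decitabine with venetoclax. It covers a longer interval than 14 days and counts deaths only, so it serves as a low anchor for loss from any cause. The other values are assumptions.

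- P(at least one of 42 treated dropped) = 1 - (1 - d)^42
- Expected number dropped of 42 treated = 42 x d
- Number treated to obtain 42 nivolumab recipients = 42 / (1 - d), rounded up
- P(at least one of 6 at a dose level) = 1 - (1 - d)^6

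| d (assumed) | P, of 42 | Expected of 42 | Treated for 42 recipients (dropped) | P, of 6 |
|---|---|---|---|---|
| 3.6% | 0.786 | 1.5 | 44 (2) | 0.197 |
| 5% | 0.884 | 2.1 | 45 (3) | 0.265 |
| 10% | 0.988 | 4.2 | 47 (5) | 0.469 |
| 15% | 0.999 | 6.3 | 50 (8) | 0.623 |

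These probabilities say how likely it is that the rule removes someone. They do not measure the bias; step 3 does.

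**The case against.** The strongest reply is that these sentences are bookkeeping for dose finding. Section 6.3.1 sits under the definition of dose-limiting toxicity, refers to the DLT period and is paired with replacement. Section 2.5.4 says that the doublet is already in clinical use and that nivolumab is the new element, so a patient without nivolumab never received the triplet. Much of this stands for the DLT set. Section 6.1 adds to it: venetoclax and decitabine are the same on Days 1-14 at all three dose levels, so early events do not help to separate them. But 6.3.1 says safety as well as DLT, 9.1 repeats the restriction for toxicity in general, and no other toxicity set is defined. Replacing a patient in the 3+3 does not require removing that patient from the safety summary.

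A second reply is that nothing is hidden. This limits the point, and several stronger readings that a reader might infer are not supported:

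- **All toxicity on Days 1-14 is left out.** The text excludes patients, not periods. Only the DLT window starts with nivolumab. Early events in patients who later receive it are not barred from toxicity tables.
- **Early tumour lysis makes a patient non-evaluable.** It does not in itself. Section 7.1.1 lets drugs be held and resumed, and a patient who recovers and receives any nivolumab is counted.
- **Early deaths disappear.** Overall survival is a secondary objective (1.2.5), so Section 9.3 brings them into an all-patient report, and Section 10.3.4 requires each to be reported.
- **Those lost are mainly the worst cases.** The documents do not say so. Withdrawal or progression would also remove patients.

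**Conclusion.** The point holds for a defined group: treated patients who die or permanently stop before any nivolumab. They are in no toxicity analysis set, so the toxicity summary for the primary objective is conditional on reaching the first nivolumab dose. For death before Day 15 the effect is certain in direction, since the summary can show none. For other toxicity the understatement is at most the share lost, and its direction rests on the reasons for stopping.

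That share is not stated. Under an assumed 3.6% to 15%, the chance that at least one of 42 treated patients is dropped is about 79% to over 99%. The range is illustrative and is not an estimate from the documents.

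Neither a failure of data capture nor a defect in starting the DLT window with nivolumab follows from this. The change should be made because it affects what the primary safety result describes and costs almost nothing.

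**What to change.** In Sections 9.1 and 6.3.1, define two sets.

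- **Safety set:** all patients who receive any dose of decitabine, venetoclax or nivolumab. Use it for every toxicity and death table, counting from Day 1 of cycle 1. Showing the time before the first nivolumab dose separately would keep the two parts distinguishable.
- **DLT-evaluable set:** patients who received nivolumab and either had a DLT or completed the observation period. Use it for the 3+3 only. This also aligns 6.3.1, which counts anyone treated during the window, with the rule in 9.1 that replaces non-completers without a DLT.

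Report the number of patients replaced before the first nivolumab dose, with the reason for each.

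The cost is a few sentences in two sections. Adverse events after baseline are already collected, so no new data are needed, and neither treatment nor the 3+3 decision rules change.
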